#### **6.2.8.3 Emesis**

Subjects that experience emesis within 4 hours of dosing will be excluded from the PK analysis for the period during which the emesis occurred.

QMD Ref: Worldwide-TMP-ST-006-4.0 Effective: 12Aug2019	Governing QMD: Worldwide-SOP-ST-001
Confidentiality Statement	

This document is the property of Worldwide Clinical Trials Inc. and may not be duplicated, copied, altered or removed from company without prior approval from Worldwide Quality Assurance or in compliance with Worldwide Standard Operating Procedures.

Worldwide Clinical Trials Controlled Quality Management Document		
 WORLDWIDE CLINICAL TRIALS	Sponsor: Protocol Number:	TB Alliance Pa-824-CL-011
STATISTICAL ANALYSIS PLAN – PHASE 1		

#### **6.2.8.4 Unable to Complete FDA Standard Breakfast**

Subjects in Panel 1 that are unable to complete the high-calorie, high-fat FDA breakfast will be excluded from PK analysis during which the incomplete breakfast occurred.

#### **6.2.8.5 Quantifiable Predose Concentrations**

If a quantifiable predose plasma concentration is identified, the following procedures will be followed:

- If the quantifiable predose concentration is less than 5% of the respective  $C_{max}$ , the value will be included in the concentration-time, PK, and statistical analysis without adjustment,
- If the predose concentration is greater than 5% of the respective  $C_{max}$ , the concentration-time data for the subject in question will be excluded from concentration-time analysis (mean and individual plots; concentration time tables), PK and statistical analyses. Quantifiable predose concentrations that are greater than 5% of the respective  $C_{max}$  will be retained in the concentration-time listing. If there are several instances of predose concentrations being greater than 5% of the respective  $C_{max}$  value, additional tables or statistical tests may be warranted and will be discussed with the Sponsor prior to final PK analysis.

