**Criteria for evaluation:**

*Pharmacokinetics:*

Full pharmacokinetic profiles of pretomanid will be determined up to 96 hours after each intake of pretomanid. Blood samples for analysis of pretomanid concentrations will be drawn just before drug intake (pre-dose), and at 0.5, 1, 2, 3, 4, 6, 8, 12, 16, 24, 36, 48, 72, and 96 hours post dose (15 samples per dose).

Primary pharmacokinetic measures include  $T_{max}$ ,  $C_{max}$ ,  $AUC_{0-t}$ , and  $AUC_{0-inf}$ . Secondary pharmacokinetic measures include the ratio of  $AUC_{0-t}$  to  $AUC_{0-inf}$ ,  $T_{1/2}$ ,  $K_{el}$ ,  $Cl/F$  and  $Vd/F$ .

Statistical summaries for a given period will include data from all subjects for whom it was a completed period, even those who do not complete all four periods. The primary mixed-model analyses for relative bioavailability, dose, and food will use all the data from all completed periods.

Descriptive statistics will be used to summarize pretomanid plasma concentrations at each sampling time point and for derived plasma PK parameters, as applicable. Statistics include sample size (n), mean, SD, percentage coefficient of variation (% CV), geometric mean, median, minimum, and maximum.

All data will be listed, even if not used for statistical summaries or model-based analyses. But data that do not come from completed periods will be characterized in the listing as to their deficiency.

For each participant, pretomanid plasma concentration-time data will be graphically presented. Similarly, graphs of the mean plasma concentration-time profiles and overlay graphs with combined

Protocol Pa-824-CL-011 V.1.0

individual plasma concentration-time profiles will be produced. Additionally, pharmacokinetic parameters may be explored graphically.

The bioavailability of 4 x 50-mg dispersible tablets relative to the 200-mg reference tablet will be determined separately for each panel using a mixed model with the log transformed PK parameter ( $C_{max}$ ,  $AUC_{0-t}$ , and  $AUC_{0-inf}$ ) as response variable; sequence, period, and treatment as fixed effects; and participant as random effect.

The effect of dose on the relative bioavailability of the dispersible tablet will be determined separately for each panel using the same model as above.

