**Table 1 Identity of Investigational Products**

Reference Product: Treatment A	Pretomanid (PA-824) Dose = 1 x 200-mg tablet (using the immediate release formulation), orally administered TB Alliance
Test Product: Treatment B:	Pretomanid (PA-824) Dose = 4 x 50-mg dispersible tablets (200 mg total), orally administered (as dispersion in water) TB Alliance
Test Product: Treatment C:	Pretomanid (PA-824) Dose = 1 x 50-mg dispersible tablet, orally administered (as dispersion in water) TB Alliance
Test Product: Treatment D:	Pretomanid (PA-824) Dose = 1 x 10-mg dispersible tablet, orally administered (as dispersion in water) TB Alliance

Each study treatment administration will be separated by a washout period of 7 days. An outpatient safety follow-up visit is planned approximately 7 days following the last pharmacokinetic sample in the last treatment period (or after drop-out).

During each study period, 120 mL blood samples will be obtained before study drug administration and at selected times through 96 hours after study drug administration. A total of 60 pharmacokinetic blood samples will be collected from each subject, 15 samples in each study period. Plasma pharmacokinetic samples will be analyzed for pretomanid using a validated analytical method. Appropriate pharmacokinetic parameters will be calculated for each formulation using non-compartmental methods.

Food and water consumption will follow the guidelines in [Section 5.4](#). Subjects who withdraw from the study will not be replaced.

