**Table 1: Treatment Schedule**

Sequence (n=24 subjects per panel)	Treatment Periods			
	Period 1	Period 2	Period 3	Period 4
ABCD	A	B	C	D
BDAC	B	D	A	C
CADB	C	A	D	B
DCBA	D	C	B	A

Treatment A (reference) = 200 mg given as a single 200 mg tablet (using the immediate release formulation), orally administered.

Treatment B (test) = 200 mg given as four 50-mg tablets (using the dispersible pediatric formulation), orally administered.

Treatment C (test) = single 50-mg dispersible tablet, orally administered.

Treatment D (test) = single 10-mg dispersible tablet, orally administered.

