## 6.10 Statistical Analyses of Pharmacokinetic Data

### 6.10.1 Relative Bioavailability

The bioavailability of 4 x 50 mg dispersible tablets (Treatment B) relative to the 200-mg reference tablet (Treatment A) will be determined separately for each panel using a mixed model with log transformed PK parameters ( $C_{max}$ ,  $AUC_{0-t}$ , and  $AUC_{0-inf}$ ) as response variable; sequence, period, and treatment as fixed effects; and subject as random effect. The effect of dose on the relative

QMD Ref: Worldwide-TMP-ST-006-4.0 Effective: 12Aug2019	Governing QMD: Worldwide-SOP-ST-001
Confidentiality Statement	
This document is the property of Worldwide Clinical Trials Inc. and may not be duplicated, copied, altered or removed from company without prior approval from Worldwide Quality Assurance or in compliance with Worldwide Standard Operating Procedures.	

Worldwide Clinical Trials Controlled Quality Management Document		
 WORLDWIDE CLINICAL TRIALS	Sponsor: Protocol Number:	TB Alliance Pa-824-CL-011
STATISTICAL ANALYSIS PLAN – PHASE 1		

bioavailability of the dispersible tablets (Treatments B, C, and D) will be determined separately for each panel using a power model (Smith, 2000) of the following general form,

$$\ln(\text{PK}) = \ln(\beta_0) + \beta_1 \cdot \ln(\text{Dose}) + \varepsilon,$$

Where

PK is the pharmacokinetic parameter tested (e.g.  $C_{\max}$  or AUC)

$\ln(\beta_0)$  is the y-intercept,

$\beta_1$  is the slope (a value of  $\beta_1 \approx 1$  indicates linearity), and

$\varepsilon$  is an error term

The estimate of  $\beta_1$  with the 90% CIs will be reported along with the dose range for proportionality.

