## 7 CHANGES TO PLANNED PROTOCOL ANALYSIS

No changes to the planned analyses have been identified.

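### The SAP's pre-dose rule is triggered by one period but, as worded, removes all of the subject's data, including valid A and B profiles

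*SAP*

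**What the plan says.** SAP 6.2.8.5 sets out two cases for a quantifiable pre-dose concentration. Below 5% of the *respective* Cmax, the value stays in without adjustment. Above 5%, "the concentration-time data for the subject in question will be excluded from concentration-time analysis" and also from the PK and statistical analyses. A further sentence, beginning "If there are several instances of predose concentrations being greater than 5% of the respective", provides for possible extra tables or tests and a discussion with the sponsor.

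The other places that bear on this are:

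- **SAP 6.2.8.3 (emesis).** Affected subjects "will be excluded from the PK analysis for the period during which the emesis occurred".
- **Protocol synopsis, criteria for evaluation.** "The primary mixed-model analyses for relative bioavailability, dose, and food will use all the data from all completed periods".
- **SAP 7.** "No changes to the planned analyses have been identified".
- **SAP 6.10.1.** B is compared with A separately in each panel, "using a mixed model with log transformed PK parameters", with sequence, period and treatment fixed and subject random.
- **SAP Table 1.** The sequences are ABCD, BDAC, CADB and DCBA. A and B are 200 mg and C is 50 mg. For the lowest dose: "Treatment D (test) = single 10-mg dispersible tablet, orally administered".
- **Protocol Section 3.** "Each study treatment administration will be separated by a washout period of 7 days".

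**The concern.** The test concerns one profile, but the stated consequence attaches to the subject and has no period limit. Every subject takes all four treatments, so a literal reading discards up to four profiles because of one.

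The design makes this more than a matter of style. Doses differ 20-fold, and D comes directly after a 200-mg dose in BDAC (after B) and CADB (after A). Carry-over is therefore most likely to exceed 5% of Cmax in the D period. D is not part of the B-versus-A contrast, and a raised pre-dose value in that period says nothing about whether the same subject's A and B profiles are valid.

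At stake are the precision and sequence balance of the primary comparison, because the losses would come mainly from two of the four sequences. The study is also open-label, so an exclusion rule for the primary analysis is better fixed by its wording than interpreted once concentrations are known.

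**Working it through.** The plan has no sample-size or precision figure to reproduce; SAP 4 and Protocol 5.1 say the number of subjects has no statistical basis. The check has three parts.

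**1. When a D period would breach 5%**

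Inputs from the documents are the 7-day (168 h) dosing interval and the 200-mg and 10-mg doses. Assumptions are Tmax of 4 h, mono-exponential decline, and R, the ratio of the previous dose's Cmax to the current one.

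Pre-dose/Cmax = R × 2^(−(168 − Tmax)/t½). This exceeds 0.05 when t½ > (168 − Tmax)/log2(R/0.05).

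- 200 mg then 10 mg, dose-proportional Cmax (R = 20): 164/log2(400) = 164/8.644 = 18.97 h.
- 200 mg then 10 mg, 10-mg Cmax one-tenth of the 200-mg Cmax (R = 10): 164/log2(200) = 164/7.644 = 21.46 h.
- With Tmax from 6 h down to 2 h, these become 18.7–19.2 h and 21.2–21.7 h.
- For comparison, with dose-proportional Cmax and only the preceding dose counted: 50 mg then 10 mg, 164/log2(100) = 24.7 h; 200 mg then 50 mg, 164/log2(80) = 25.9 h; equal doses, 164/log2(20) = 37.9 h.

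D after 200 mg is thus the first place the rule would fire. The documents give no half-life or quantitation limit, so the frequency cannot be determined and may be zero.

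**2. Loss of precision if it fires**

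Assume six subjects per sequence in each panel. The variance of ln(B/A), in units of the within-subject variance, comes from least squares with subject, period and treatment effects. The SAP model (subject random, between-to-within variance ratio 1 or 4) gives the same values to four decimals. SE change = sqrt(variance/0.0833) − 1.

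| Case | Profiles | df | Variance | SE change |
|---|---|---|---|---|
| No loss | 96 | 66 | 0.0833 | – |
| One subject lost (BDAC or CADB) | 92 | 63 | 0.0871 | +2.2% |
| Two lost (one from each) | 88 | 60 | 0.0913 | +4.7% |
| Five lost (2 and 3) | 76 | 51 | 0.1093 | +14.5% |
| Two D profiles only | 94 | 64 | 0.0833 | 0.0% |
| Five D profiles only | 91 | 61 | 0.0833 | 0.0% |

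Fewer subjects alone would give sqrt(24/22) − 1 = 4.4% and sqrt(24/19) − 1 = 12.4%; the remainder of the 4.7% and 14.5% is sequence imbalance. In the extreme where all of BDAC and CADB are lost, only ABCD and DCBA remain and B versus A can no longer be estimated under this model.

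**3. What that does to the interval**

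90% CI around a ratio of 100% = 100 × exp(± t(0.95, df) × sqrt(ln(1 + CV²) × variance)). The within-subject CV is not in the documents, so a range is shown. Example, CV 30% and no loss: sqrt(ln(1.09) × 0.0833) = 0.0847; times t = 1.668 gives 0.141; the interval is 86.8–115.2.

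| Assumed CV | No loss | Two lost | Five lost |
|---|---|---|---|
| 15% | 93.1–107.4 | 92.7–107.8 | 92.1–108.6 |
| 20% | 90.9–110.0 | 90.5–110.5 | 89.6–111.6 |
| 30% | 86.8–115.2 | 86.2–116.0 | 85.0–117.7 |

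**The case against.** The best reply is that the sentence already means the period. A subject has up to four Cmax values, so *respective* picks out one profile, and the later sentence counts instances rather than subjects. These documents also use *subject* loosely. Protocol 8.1 says that samples from subjects who vomit within 4 hours of dosing are not analyzed, without naming a period, and SAP 6.2.8.3 then applies this by period. SAP 6.2.8.4 omits the word *period* from the breakfast rule, while Protocol 7.4 supplies it. The contrast with the emesis rule may therefore be uneven drafting. This stands as evidence of intent, but it does not provide the missing limit.

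The synopsis argument can also be pushed too far: excluding only the D profile would itself depart from using all data from all completed periods, if that period counts as completed. That is fair, and it weakens the synopsis and SAP 7 as support. The difference is that a breached profile has a reason for exclusion and the subject's other profiles do not.

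The sponsor discussion makes silent loss of many subjects less likely. However, it applies only to several instances, concerns additional output, and does not define the unit of exclusion.

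Finally, the harm is hypothetical and small. That stands, and it limits the weight of the point.

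**Conclusion.** The point holds and is minor. The rule as written has no period limit, and nothing elsewhere in the documents supplies one for it. Followed literally, each D breach costs four profiles where one would do, and it raises the SE of the primary contrast when period-level exclusion would leave it unchanged.

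The sizes are conditional on a breach occurring, on six subjects per sequence, and on the assumed CVs. Firing in D after 200 mg needs a half-life above about 19 to 21.5 h under the stated decay assumptions. The five-subject case is an illustration, not a forecast. B/A is not expected to be biased, and because the plan sets no equivalence margin or power target, no stated criterion would be lost.

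**What to change.** Reword the second case in SAP 6.2.8.5 so that the exclusion covers that subject's concentration-time data in the affected treatment period only, and add that the subject's other completed periods stay in all analyses. This agrees with SAP 6.2.8.3 and Protocol 7.4.

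The cost is a few words, with no new data and no new analysis. The SAP supplement describes changes made after database lock and leaves the SAP text unaltered, so a change now would need a further supplement. If the SAP can no longer be revised, the clinical study report should state which unit of exclusion was applied and whether any pre-dose value triggered the rule.

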### **6.3 Conventions**

All clinical data listings, summaries, figures and statistical analyses will be generated using SAS (Version 9.4 or higher).

Summaries of the clinical data will be presented by treatment panel and treatment group or overall. PK data listings, summaries, figures, and statistical analyses will be generated using Phoenix™ WinNonlin® (Version 8.1 or higher) or SAS (Version 9.4 or higher). PK concentration data will be summarized by panel and treatment at each nominal sample time. PK parameter data will be summarized by panel and treatment.

Treatment panel labels will be displayed as follows:

Panel 1	Panel 2
(Fed)	(Fasted)

QMD Ref: Worldwide-TMP-ST-006-4.0 Effective: 12Aug2019	Governing QMD: Worldwide-SOP-ST-001
Confidentiality Statement	
This document is the property of Worldwide Clinical Trials Inc. and may not be duplicated, copied, altered or removed from company without prior approval from Worldwide Quality Assurance or in compliance with Worldwide Standard Operating Procedures.	

Worldwide Clinical Trials Controlled Quality Management Document			
 WORLDWIDE CLINICAL TRIALS	Sponsor: Protocol Number:	TB Alliance Pa-824-CL-011	
STATISTICAL ANALYSIS PLAN – PHASE 1			

Treatment group labels will be displayed as follows:

Pretomanid 200 mg IR Tablet	Pretomanid 4 x 50-mg Dispersible Tablets*	Pretomanid 50-mg Dispersible Tablet	Pretomanid 10-mg Dispersible Tablet
--------------------------------	---	---	---

IR = Immediate Release; \*Dispersible Pediatric Formulation.

Listings will be sorted in the following order: subject number, treatment panel, treatment sequence parameter, and visit unless otherwise stated. All data will be listed.

For clinical data, continuous variables will be summarized by the number of non-missing observations, mean, median, standard deviation, and minimum and maximum.

PK data (concentration-time data and PK parameters) will be summarized by the number of non-missing observations (n), mean, standard deviation (SD), median, minimum (min), maximum (max), and coefficient of variation (CV%), calculated as  $(SD/Mean)*100$ . In addition, the geometric mean and geometric CV%, calculated as  $SQRT[\exp(SD^2 \text{ of log transformed data}) - 1]*100$ , will be reported for  $C_{max}$  and AUCs.

Categorical variables will be summarized by presenting the frequency and percent. Percentages will be based on the number of non-missing observations or the analysis set unless otherwise specified. For each variable, all categories will be shown. Zero frequencies (but not the percent) within a category will be presented.

### 6.3.1 Decimal Places

Means, medians and percentiles will be displayed to one more decimal place than the data, dispersion statistics (e.g. standard deviation) will have two more decimal places, and the minimum and maximum will be displayed to the same number of decimal places as reported in the raw data. Percentages will be displayed with one decimal place.

For PK data, individual concentrations and PK parameters will be reported to 3 significant figures. Nominal and relative times will be presented to 3 significant figures. For summary statistics, n will be reported as a whole number; mean, standard deviation, median, minimum, maximum, CV%, geometric mean, and geometric mean CV% will be reported to the same precision as for individual data. For results from the statistical comparisons, least squares (LS) means and geometric LS means will be presented to 3 significant figures, p-values will be reported to 4 decimal places, percent ratios of the geometric LS means and associated 90% confidence intervals will be reported to 2 decimal places.

QMD Ref: Worldwide-TMP-ST-006-4.0 Effective: 12Aug2019	Governing QMD: Worldwide-SOP-ST-001
Confidentiality Statement	

This document is the property of Worldwide Clinical Trials Inc. and may not be duplicated, copied, altered or removed from company without prior approval from Worldwide Quality Assurance or in compliance with Worldwide Standard Operating Procedures.

Worldwide Clinical Trials Controlled Quality Management Document		
 WORLDWIDE CLINICAL TRIALS	Sponsor: Protocol Number:	TB Alliance Pa-824-CL-011
STATISTICAL ANALYSIS PLAN – PHASE 1		

## 6.4 Subject Disposition

Subject disposition will be summarized as follows:

- The number of subjects completing the study and the number in each analysis set will be summarized by treatment panel and overall for the Randomized set.
- The number of subjects completing each treatment period will be summarized by treatment panel and overall for the Randomized set.
- The number of early withdrawals and the reasons for withdrawals will be tabulated by treatment panel and overall for the Randomized set.

## 6.5 Protocol Deviations

A listing of protocol deviations will be provided within [Appendix 16.2](#) of the CSR.

## 6.6 Baseline Comparability

The comparability of treatment panels (Fed/Fasted) with respect to subject demographics and baseline characteristics will be assessed in a descriptive manner, but no formal statistical testing will be performed.

### 6.6.1 Demographic Data

Standard continuous or categorical variable summaries will be presented by treatment panel and overall for the following variables based on the Safety Analysis Set.

- Sex (Male, Female)
- Age at Informed Consent (years)
- Ethnicity (Hispanic or Latino, Non-Hispanic or Latino)
- Race (White, Black or African American, Asian, American Indian or Alaska Native, Native Hawaiian or Other Pacific Islander, Multiple Race)
- Height at Screening (cm)
- Weight at Screening (kg)
- Body Mass Index at Screening (kg/m^2)

All demographic data will be listed.

QMD Ref: Worldwide-TMP-ST-006-4.0 Effective: 12Aug2019	Governing QMD: Worldwide-SOP-ST-001
Confidentiality Statement	

This document is the property of Worldwide Clinical Trials Inc. and may not be duplicated, copied, altered or removed from company without prior approval from Worldwide Quality Assurance or in compliance with Worldwide Standard Operating Procedures.

Worldwide Clinical Trials Controlled Quality Management Document		
 WORLDWIDE CLINICAL TRIALS	Sponsor: Protocol Number:	TB Alliance Pa-824-CL-011
STATISTICAL ANALYSIS PLAN – PHASE 1		

## 6.7 Medical History

A listing of previous and ongoing conditions at Screening will be presented for the Safety Analysis Set. Conditions will be coded using the Medical Dictionary of Regulated Activities (MedDRA version 22.0 or higher) primary system organ class and preferred term.

## 6.8 Prior and Concomitant Medications

A listing of prior and concomitant medications will be provided. Prior medications are defined as all medications starting and stopping before the date of first dose of study drug. Concomitant medications are defined as medications taken on or after the date of first dose of study drug. Each concomitant medication will be assigned to the last study drug taken prior to starting the concomitant medication. Concomitant medications taken before the first dose of study drug will be assigned to 'No Treatment'. Prior and concomitant medications will be coded using the World Health Organization (WHO) Drug Dictionary B3 – September 2019 version.

## 6.9 Exposure to Study Drug

Exposure to study medication will be tabulated by treatment panel and treatment group. All dosing information will be listed.

## 6.10 Statistical Analyses of Pharmacokinetic Data

### 6.10.1 Relative Bioavailability

The bioavailability of 4 x 50 mg dispersible tablets (Treatment B) relative to the 200-mg reference tablet (Treatment A) will be determined separately for each panel using a mixed model with log transformed PK parameters ( $C_{max}$ ,  $AUC_{0-t}$ , and  $AUC_{0-inf}$ ) as response variable; sequence, period, and treatment as fixed effects; and subject as random effect. The effect of dose on the relative

QMD Ref: Worldwide-TMP-ST-006-4.0 Effective: 12Aug2019	Governing QMD: Worldwide-SOP-ST-001
Confidentiality Statement	
This document is the property of Worldwide Clinical Trials Inc. and may not be duplicated, copied, altered or removed from company without prior approval from Worldwide Quality Assurance or in compliance with Worldwide Standard Operating Procedures.	

Worldwide Clinical Trials Controlled Quality Management Document		
 WORLDWIDE CLINICAL TRIALS	Sponsor: Protocol Number:	TB Alliance Pa-824-CL-011
STATISTICAL ANALYSIS PLAN – PHASE 1		

bioavailability of the dispersible tablets (Treatments B, C, and D) will be determined separately for each panel using a power model (Smith, 2000) of the following general form,

$$\ln(\text{PK}) = \ln(\beta_0) + \beta_1 \cdot \ln(\text{Dose}) + \varepsilon,$$

Where

PK is the pharmacokinetic parameter tested (e.g.  $C_{\max}$  or AUC)

$\ln(\beta_0)$  is the y-intercept,

$\beta_1$  is the slope (a value of  $\beta_1 \approx 1$  indicates linearity), and

$\varepsilon$  is an error term

The estimate of  $\beta_1$  with the 90% CIs will be reported along with the dose range for proportionality.

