## **8.2 Pharmacokinetic and Statistical Analyses**

Primary pharmacokinetic measures include  $T_{max}$ ,  $C_{max}$ ,  $AUC_{0-t}$ , and  $AUC_{0-inf}$ . Secondary pharmacokinetic measures include the ratio of  $AUC_{0-t}$  to  $AUC_{0-inf}$ ,  $T_{1/2}$ ,  $K_{el}$ ,  $Cl/F$  and  $V_d/F$ .

All evaluable subjects completing at least one treatment period will be included in the pharmacokinetic analysis.

Descriptive statistics will be used to summarize pretomanid plasma concentrations at each sampling time point and for derived plasma PK parameters, as applicable. Statistics include sample size (n), mean, SD, percentage coefficient of variation (%CV), geometric mean, median, minimum, and maximum.

For each participant, pretomanid plasma concentration-time data will be graphically presented. Similarly, graphs of the mean plasma concentration-time profiles and overlay graphs with combined individual plasma concentration-time profiles will be produced. Additionally, pharmacokinetic parameters may be explored graphically.

The bioavailability of 4 x 50 mg dispersible tablets relative to the 200-mg reference tablet will be determined separately for each panel using a mixed model with the log transformed PK parameter ( $C_{max}$ ,  $AUC_{0-t}$ , and  $AUC_{0-inf}$ ) as response variable; sequence, period, and treatment as fixed effects; and participant as random effect.

The effect of dose on the relative bioavailability of the dispersible tablet will be determined separately for each panel using the same model as above.

The effect of food on the relative bioavailability of pretomanid will be determined comparing, across panels, each formulation and dose taken after eating breakfast versus

Protocol Pa-824-CL-011 V1.0

the same formulation and dose taken in fasted conditions using a mixed model with the log transformed PK parameter as response variable; panel, sequence, period, treatment, and panel-by-treatment interaction as fixed effects; and participant as random effect.

The  $T_{max}$  of pretomanid for each of the formulations will be descriptively compared.

Other statistical models and/or population pharmacokinetic modelling may also be used for further data interpretation.

Pharmacokinetic calculations will be performed using appropriate software.

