## 1 INTRODUCTION

This document details the planned statistical analyses for TB Alliance, protocol “Pa-824-CL-011” study titled “An Open-label, Randomized, Four-period Crossover Study in Two Panels of Healthy Adult Participants to Assess the Relative Bioavailability, Food Effect, and Dose-dependence of Single-Dose Immediate-Release and Single-dose Dispersible Formulations of Pretomanid”. The proposed analyses are based on the contents of the final version of the protocol (dated 06-Dec-2019).

This is a single-dose, open-label, randomized, four-period, four-treatment, crossover study in healthy adult subjects. Each panel of 24 subjects will be randomized according to the same 4-sequence, 4-period Williams design, in which each participant will receive four single-dose treatments. Subjects in Panel 1 will receive all treatments after consuming an FDA standard high-fat, high-calorie breakfast following an overnight fast of at least 10 hours. Subjects in Panel 2 will receive all treatments directly following an overnight fast of at least 10 hours. The two panels will be investigated concurrently. The maximum duration of the study from screening to study exit will be approximately 54 days.

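### SAP 6.10.1 writes the dose-effect power model with no subject term, an undeclared change from the protocol's mixed model; fitted as written, its 90% CI for the slope does not have 90% coverage in general.

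*SAP*

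**What the plan says.** The protocol treats dose as a mixed-model question. Its synopsis (Criteria for evaluation) states: "The primary mixed-model analyses for relative bioavailability, dose, and food will use all the data from all completed periods". Section 8.2 is specific: "The effect of dose on the relative bioavailability of the dispersible tablet will be determined separately for each panel using the same model as above". In the model it points back to, sequence, period and treatment are fixed effects and participant is random.

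SAP 6.10.1 keeps that structure for B versus A, with "sequence, period, and treatment as fixed effects; and subject as random effect". For dose it changes model; the dose effect on the "bioavailability of the dispersible tablets (Treatments B, C, and D) will be determined separately for each panel using a power model". The equation, "of the following general form", is ln(PK) = ln(β0) + β1·ln(Dose) + ε, where ε "is an error term". No subject, period or sequence term is named. What is reported is the estimate of β1 "with the 90% CIs will be reported along with the dose range for proportionality".

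SAP section 7 records no change from the protocol's analyses, and the SAP supplement alters no text. SAP section 8 lists two software entries and omits the methods paper cited for the power model.

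**The concern.** Under SAP Table 1 every subject is scheduled to receive B (200 mg), C (50 mg) and D (10 mg). The power model therefore uses three values per subject, and these share whatever makes that subject's exposure high or low. A regression with one error term treats the 72 values in a panel as independent. It puts between-subject variation into the residual although dose is compared within subjects, and it ignores any variation between subjects in the slope. The first error widens the interval and the second narrows it.

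The slope and its CI are the stated result for the secondary objective on dose and bioavailability. Tables 14.4.6 and 14.4.7 are the only inferential dose-effect tables listed. Protocol 1.3 says these tablets are to be used for weight-adjusted dosing in children under 12. Two programmers could also fit different models from the same text and report different intervals.

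**Working it through.** **Inputs from the documents.** 24 subjects per panel; doses 10, 50 and 200 mg; two-sided 90% CI. No variance, CV or correlation is given (SAP section 4 says that the sample size has no statistical basis), so there is no stated figure to reproduce and all variance inputs below are assumptions.

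**Design constants.** With x = ln(10), ln(50), ln(200), the sum of squares about the mean is Sxx = 4.4955 per subject, and 24 × 4.4955 = 107.89 per panel. Error degrees of freedom are 70 as written, 47 with a subject intercept, and 23 with a random intercept and slope.

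**Variances.** Let sw², sb² and ss² be the within-subject, between-subject and slope variances of ln(PK). Dividing by 107.89 gives the variance of the slope.

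- The as-written fit estimates about sw² + sb² + ss²·Sxx/3.
- The correct value is sw² + ss²·Sxx.

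**Case 1: one common slope (ss = 0).** The as-written standard error is too large by about 1/√(1 − ICC), so coverage is about 2Φ(1.645/√(1 − ICC)) − 1. At ICC 0.5 this is 2Φ(2.326) − 1 = 98.0%. Simulation, 20,000 runs per setting:

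| ICC | 0 | 0.1 | 0.2 | 0.3 | 0.5 | 0.7 | 0.8 |
|---|---|---|---|---|---|---|---|
| CI width, as written ÷ subject-adjusted | 1.00 | 1.05 | 1.11 | 1.19 | 1.40 | 1.80 | 2.20 |
| Coverage as written | 90% | 92% | 93% | 95% | 98% | 99.6% | 99.9% |

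With 10% of observations missing at ICC 0.69, as-written coverage was 99.1% (6,000 runs).

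**Case 2: slopes vary between subjects.** Simulated coverage with within-subject CV 20%:

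| Slope SD | 0 | 0.05 | 0.10 | 0.15 | 0.20 |
|---|---|---|---|---|---|
| As written, between-subject CV 20% | 97.7% | 96.3% | 91.5% | 85.5% | 80.9% |
| As written, between-subject CV 30% | 99.5% | 98.9% | 96.1% | 92.0% | 86.6% |
| As written, between-subject CV 40% | 99.9% | 99.7% | 98.6% | 95.5% | 91.2% |
| Random intercept only (CV 20%) | 90.1% | 88.2% | 84.0% | 80.5% | 79.3% |
| Random intercept and slope (CV 20%) | 90.1% | 90.3% | 90.1% | 89.9% | 89.9% |

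Hand check at slope SD 0.20 and both CVs 20%: sw² = sb² = ln(1.04) = 0.0392. The as-written variance is 0.0784 + 0.04 × 4.4955/3 = 0.1384; the correct one is 0.0392 + 0.04 × 4.4955 = 0.2190. Coverage is about 2Φ(1.645 × √(0.1384/0.2190)) − 1 = 81%.

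**Where the error changes sign.** Setting the two variances equal gives ss = sb/√(2 × 4.4955/3) = 0.578·sb, whatever the within-subject CV. That is a slope SD of 0.11, 0.17 and 0.22 at between-subject CVs of 20%, 30% and 40%.

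**Scale of the result (both CVs 20%).** The half-width for β1, as written versus the proposed fit, is 0.045 versus 0.034 at slope SD 0, and 0.059 versus 0.076 at slope SD 0.20. Over the 20-fold dose range, 20 raised to the half-width gives upper multipliers of 1.14 versus 1.11, and 1.19 versus 1.26.

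**The case against.** **The text may not exclude a subject effect.** The equation is described as a general form, it follows a sentence naming subject as random, and SAP section 1 says: "The proposed analyses are based on the contents of the final version of the protocol (dated 06-Dec-2019". This stands as a possible reading. It makes the specification ambiguous, and the reference that might settle it is not listed. The interval result is therefore conditional on fitting the equation as written. The change from a treatment-factor model to a power model is undeclared on either reading.

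**The usual error is conservative.** This is largely right. Of the 15 as-written coverages in Case 2, 12 exceed 90%. Under-coverage needs slope SDs of 0.15 or more, for which the documents offer no evidence; an SD of 0.20 means about a 1.8-fold change (20^0.20) in dose-normalised exposure across the range. But an over-wide interval discards the precision that the crossover provides and makes real non-proportionality easier to miss.

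**Restoring the protocol's random participant effect alone would not cure under-coverage.** Also right: with varying slopes, the intercept-only fit covers less than the as-written one at both CVs 20%. Under-coverage is thus not due to leaving the protocol's error structure. This is why the remedy needs a random slope.

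**The protocol permits other models.** Section 8.2 allows them for further interpretation. That covers additions, not an unrecorded replacement of the planned analysis.

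**The impact is limited.** The objective is secondary, there are no acceptance limits, and B versus A is unaffected. Listing 16.2.6.8 will show the fitted model afterwards, but that does not amount to pre-specification.

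**Conclusion.** The concern holds. The departure from protocol 8.2 is certain and undeclared. The SAP names no subject term for a model fitted to repeated measurements on the same people. If fitted as written, the nominal 90% CI for β1 has its stated coverage only when subjects do not differ, or by coincidence near a slope SD of 0.58 times the between-subject SD. Over the assumed ranges, actual coverage ran from about 81% to 99.9%, and a reader cannot tell which side applies.

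These sizes assume normal random effects, with subject slopes independent of the subject mean at mid log dose, and complete data except where stated. The slope estimate averaged 1.000 against a true value of 1 throughout, so the fault lies in the interval. A power model is itself a reasonable choice for dose proportionality. The change should be made, but it does not affect the primary objective.

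**What to change.** In SAP 6.10.1, state the full model. Within each panel, fit ln(PK) on ln(Dose) for B, C and D with a random subject intercept and a random subject slope, keep the protocol's sequence and period fixed effects, and name the degrees-of-freedom method (for example Kenward-Roger). State a fallback to random intercept only if the slope variance is estimated as zero or the fit does not converge. Report β1 and its 90% CI from that fit.

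Record in SAP section 7 that the power model replaces the protocol's treatment-effect model, and why. The SAP supplement was itself issued after database lock, so if the change comes that late the record belongs in the clinical study report, marked as made after lock. Add the cited methods paper to SAP section 8.

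**Cost.** Wording and a few lines of code; no new data. If slopes do not vary, the CI is about 1.5% wider than with a random intercept only, or 5% wider under the fallback rule. With within-subject CV 20%, the slope variance was estimated at or below zero in 50%, 27%, 4% and 0% of runs at slope SD 0, 0.05, 0.10 and 0.20, so the fallback will be used often when slopes barely vary. Coverage with the fallback stayed between 89.7% and 91.8% across five CV settings. Those runs used complete data, without period or sequence terms and without Kenward-Roger. A separate exact calculation showed that, with six subjects per sequence and complete data, adding sequence and period leaves the standard error of the slope unchanged.
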